## 6. SCIENTIFIC CONSIDERATIONS

### Research studies

Richmond collaborates with phase 4 clinical studies and therapeutic equivalence (bioavailability-bioequivalence) with its own drugs in Argentina, especially in infectious diseases such as HIV, complying with current ANMAT (National Administration of Medicines, Food, and Medical Technology) regulations. Bioequivalence studies are mandatory in Argentina in order to obtain marketing authorization. These studies have been published in several conferences and are available to the medical community. Some of them are listed below:

**Table 2. Clinical studies related to Richmond**

Name/objective	Author	Published	Contribution of Richmond
Andes—evaluate the safety, tolerability, and antiviral efficacy of DRV/r and 3TC versus DRV/r therapy with 3TC and Tenofovir or FTC and TDF in HIV-1 infected subjects without prior treatment in adults	Huésped-Pedro Cahn Foundation	(Conference on Retroviruses and Opportunistic Infections) 2018, Boston	140 Darunavir/Ritonavir 800/100mg treatments

Product: 910002

Study of Comparative bioavailability of darunavir 800 mg in the presence ritonavir in healthy volunteers	CRO Clínica F.P. Clinical Pharma S.R.L.	2014 study, for marketing in Argentina	Funded by Richmond Argentina
Comparative bioavailability study of darunavir 600 mg in the presence of ritonavir in healthy volunteers	Clinical CRO F.P. Clinical Pharma S.R.L.	2014 study, for marketing in Argentina	Funded by Richmond Argentina
Bioequivalence study of two formulations containing the combination of Efavirenz 600 mg, Emtricitabine 200 mg, and Tenofovir Disoproxil Fumarate 300 mg, single oral dose in healthy volunteers.	Center of the Mutual Association of Professionals of the Italian Hospital	2017 study, for marketing in Argentina	Funded by Richmond Argentina
Single-dose bioequivalence study of Previd® / Vyvalto® in healthy volunteers	CRO Clínica F.P. Clinical Pharma S.R.L. at CIAREC Clinic	2018 study, for marketing in Argentina	Funded by Richmond Argentina
Dual therapy with fixed dose combination of Darunavir/Ritonavir plus	Helios Salud, Buenos Aires, Argentina F. Rombini, D.M. Cecchini, A.	Published in EACS 2019 – Annual Meeting of the European AIDS Clinical Society	Darunavir/Ritonavir 800/100mg treatments

Product: 910002

Raltegravir in HIV-infected patients in Argentina	Urueña, C. Vecchio, M. Huberman, I. Cassetti.		
---	--	--	--

Information available from the Medical Affairs Department

### Selection of research centers

In Colombia, Richmond will hire research centers that meet the highest standards in their field, are approved by Invima, and comply with national and international regulations to carry out experimental therapeutic studies.

At Richmond, we have appointed the following members to select the research center:

Position	Country
Richmond General Manager	Colombia
Operations Manager and Technical Director	Colombia
Scientific Liaison Physician	Colombia
Medical Affairs Manager	Argentina supports Colombia
Director of Scientific and Technical Affairs	Argentina supports Colombia

The Medical Affairs Department at Richmond Argentina prepares a summary presentation, sufficiently substantiated, of the project or preliminary draft to be presented to the Research Centers, which is selected according to:

1. A proposal that can answer the research question
2. The deadlines for the project are met.
3. Compliance with Richmond's budget.

### Clinical Trial Monitor

When required, Richmond, as sponsor, will hire a clinical study monitor who will be responsible for supervising and controlling the quality of the data arising from the trials, who will be responsible for the sponsor's interaction with the site where the research is conducted, and who will be part of the research team. This person must have experience in conducting clinical studies or trials, be a healthcare professional, and have completed courses in Good Clinical Practices and other studies required for this purpose. They must also demonstrate teamwork skills, commitment, organization, and planning abilities.

### Authorship and Intellectual Property

Product: 910002

For all intents and purposes, the authorship and, therefore, the moral rights of the research requested by Richmond shall belong to the Research Center and the researchers it designates to carry it out. In each publication or reference made to the study, it shall be indicated that the study was conducted on behalf of the Research Center, regardless of whether Richmond makes the corresponding citation. The economic rights of the research shall belong to Richmond in its capacity as sponsor.

## **7. PROTECTION OF SUBJECTS**

### **Characteristics of participating subjects**

People who are tested to get results on compounds or products being studied by research centers doing studies for Richmond should always do it voluntarily and freely. They shall be selected by the respective research center according to the needs of the study, ensuring, in all cases, optimal safety conditions and conducting prior health checks to establish the best possible safety conditions for each participant.

### **Informed Consent**

Each participant must sign a document containing a clear explanation of the studies to which they will be subjected and their characteristics, indicating any possible consequences that may arise from their completion, the insurance mechanisms, the manner in which any anomalies that may arise must be communicated to the research center, clearly and expressly indicating that they consent to participate in the study, for the time and under the conditions required by the study, freely and spontaneously, for which they have received sufficient and clear information necessary to express their acceptance.

To this end, the research center will carry out all necessary activities and procedures to provide each participant with all the information they need to participate in the study, and this will be reported in the document mentioned in the preceding paragraph.

### **Confidentiality**

The Informed Consent form that is signed will also set out the unconditional commitment undertaken by the research center and Richmond to maintain the confidentiality of the clinical and medical information obtained from each participant as a result of the study, in accordance with the provisions in force in relation to the confidentiality and handling of medical records applicable in the country.

Likewise, the participant shall undertake to maintain confidentiality with respect to any confidential information to which they may have access as a result of the study in relation to the research center, Richmond, its activities, policies, methods, and other information that has been expressly determined by them to be subject to confidentiality of any kind.

Product: 910002

General information on participating subjects derived from studies conducted by Richmond and a Research Center will be treated in accordance with current regulations, as described in Table No. 1.

Richmond Laboratories aims to use its Corporate Code of Conduct and Ethics and Confidentiality Agreement to promote good judgment and integrity among its employees and protect the personal data to which it has access, under penalty of incurring liability in accordance with applicable regulations.

When a study or research project is conducted, Richmond, as the project sponsor, will appoint a representative with the appropriate training to carry out the study.

## **7. FINANCIAL CONSIDERATIONS**

In carrying out the manufacturing, technical, and commercial activities of LABORATORIOS RICHMOND COLOMBIA S.A.S., the company obtains the resources that first cover its costs and expenses, meet the company's tax obligations, and subsequently contribute a surplus for the recognition of any dividends that may be paid to shareholders.

As part of these activities and to promote the improvement of the quality of its products, the effectiveness of its services, and the safety of its end consumers, all under conditions of efficiency and sustainable profitability for the company, LABORATORIOS RICHMOND COLOMBIA S.A.S. allocates part of the resources obtained from its activity to the development of studies, analyses, and research that allow it to access the improvements required by the various areas of the company, especially with regard to refining its technical knowledge aimed at optimizing its products and providing the public with the best quality within its economic means.

It is therefore a matter of having its own resources for research, analysis, and development within the framework of the highest standards of ethics and commitment to patient health, providing them with safe, affordable, effective, and state-of-the-art medicines, objectives that are achieved by allocating enormous resources obtained in the daily exercise of its activity to research and studies based on the high principles and standards described in this document.

It should be noted that for LABORATORIOS RICHMOND COLOMBIA S.A.S. and its shareholders, it is vital that in the relationships it establishes with its business partners, public officials, the general public, and other stakeholders, they can trust the accuracy and integrity of the financial and other information we publish. Internally, it is also essential to have reliable information so that we can make informed decisions and comply with the objectives set out, with the corresponding legislation, respecting the obligations regarding the publication of information.

Our books and records accurately and clearly reflect our transactions, with a reasonable level of detail and in accordance with our accounting practices and policies.

Product: 910002

Some employees have specific responsibilities in this area, although we all contribute to the process of recording business results and maintaining records, and all employees are responsible, to the extent of their competencies, for helping to ensure that the information we record is accurate, timely, complete, and maintained in a manner consistent with our internal control system.

In addition, we exercise special care with regard to money laundering, which is a huge global problem with serious consequences. The set of mechanisms or procedures aimed at giving the appearance of legitimacy or legality to goods or assets of uncertain origin would undermine our integrity, damage our reputation, and could expose RICHMOND and its employees to serious financial and criminal penalties. Therefore, it is vital in the performance of our activities that, when faced with situations that may arise, we take special precautions that we adhere to strictly at all times.

It is a recognized fact that the expectations of both trial participants and investigators can influence the assessment of the response to the intervention, thus influencing the results, as they carry a risk of classification bias. This is why masking or blinding techniques are used(27).

Blinding therefore prevents the researchers' preferred intervention from being favored in the assessment(28). Even if the researcher is impartial, the initial results obtained may influence expectations for subsequent results. In addition, participants also assess the effects, whether beneficial or adverse, differently if they know which intervention group they have been assigned to. Furthermore, if a subject knows that they are assigned to the placebo group, they may modify their behavior because they "feel unprotected," a phenomenon called decontamination, which is a significant problem, especially in lifestyle studies(27).

In this way, blinding is complemented by randomization to try to ensure the objectivity and impartiality of researchers and trial participants. These masking techniques can be performed at different levels, which we describe below(27).

*Open-label or non-blinded trial*

Sometimes, the nature of the intervention makes it impossible to conceal it from participants. Consider, for example, a surgical intervention or treatment with a drug that has obvious or recognizable toxicity. Another example where masking can sometimes be difficult is in the case of non-pharmacological interventions, although there are strategies that help to solve the problem. On other occasions, it is unethical to mask, such as when invasive placebos are required (e.g., parenteral injections in children). In these cases, what is called an open-label, non-blind study is conducted, but we can always resort to blinding other participants, such as those who collect the data or those who perform the statistical analysis. This is called a blinded evaluator(29).

Product: 910002

*Simple blind*

In this case, the researchers or, more commonly, the participants are unaware of the intervention each one is receiving(27).

*Double-blind*

Both the participants and the researchers in the trial do not know which group each of the trial participants has been assigned to(27).

The study will be conducted using double-blind masking. The Nifedipine Comparator and Nifedipine Richmond products will be packaged identically so that treatment masking is maintained. Thus, the volunteer, the investigator, and the staff involved in the clinical evaluation of the participants will not know the group assignments.

*Triple-blind*

In this case, in addition to those already mentioned, the person analyzing the data or responsible for monitoring and suspending the study is also unaware of which group each participant has been assigned to. An extended variant of this masking, called "quadruple-blind," is also described, in which even the study sponsor does not know whether the intervention being promoted is successful until the results are published(27). It should be noted that when masking is used, protocols must be established in advance to allow the blind to be broken in the event of serious adverse effects and to facilitate the interruption of the trial for safety reasons, if necessary.

According to RESOLUTION 2378 OF 2008, which adopts Good Clinical Practices for institutions conducting research with drugs in humans, this protocol complies with its guidelines:

Ensure that study personnel are familiar with and properly handle the investigational product through the following actions:

- a) Training of persons responsible for handling and dispensing the product.
- b) Written delivery of procedures and instructions for handling and storing the study drug, specifying: 1. Procedure for proper and safe receipt of drugs. 2. Storage conditions. 3. Method of delivery to participants.
- 4. Final disposal of medication not used in the study Review of accounting records for the investigational product.

Availability of safety and efficacy data from previous clinical or preclinical studies to support its administration in humans. a) Route of administration b) Dosage c) Time period d) Study population e) Adverse reactions f) Contraindications Investigator's protocol and manual.

Product: 910002

#### ASPECTS RELATED TO THE SPONSOR

The sponsor must obtain and document approval for the use of the study product from INVIMA (INVIMA project approval certificate).

The sponsor must ensure control of the distribution and return of the investigational product during the study. These measures include:

- a) Supplying the investigational product
- b) Maintaining records documenting the shipment, receipt, return, and destruction of the product involved in the study Delivery and return letters for the investigational product.

#### *Description*

The masking of samples of the product Nifedipine 30 mg Extended Release Capsules from Laboratorios Richmond Colombia S.A.S will be carried out in accordance with the following procedure.

#### *PRESENTATION OF SAMPLES*

##### Investigational product Comparator:

Folding box x 30 capsules. Each folding box contains 3 blister packs x 10 capsules

The capsules of this product are: Hard capsule No. 2 with a translucent blue cap and a translucent orange body.

Nifedipine Richmond:

Folding box x 30 capsules. Each folding box contains 3 blister packs x 10 capsules

The capsules in this product are: Hard capsule No. 2 with a translucent blue cap and translucent orange body.

##### Identification of samples

The reference product samples and the Nifedipine Richmond samples will be assigned a code. This code will only be known to the project leader on behalf of the Sponsor and the Pharmaceutical Chemist responsible for dispensing the medication.

The samples of the Comparator Nifedipine and Nifedipine Richmond products will be identified as follows:

Blister pack

Each blister pack containing 10 capsules will have the batch number and expiry date printed in low relief.

Product: 910002

The blister pack of the reference product and the product under study will have the following information printed on the aluminum foil:

Clinical Study Code

Generic name of the product and concentration

Batch number and expiration date

Pharmaceutical form and route of administration

Name of the sponsor

Folding box

The comparator Nifedipine and Richmond Nifedipine will be packaged in folding boxes printed with the same information as the blister pack:

Product Batch

Expiration date and storage conditions Generic name of the product and concentration

Pharmaceutical form, route of administration, and number of units Clinical Study Code

Participant Code and Visit Number Name and

Address of Sponsor

Legend: "Medication for use in clinical studies only" Legend: "Keep out of reach of children"

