#### 6.5 Treatment compliance

The investigator or assigned staff will train the participant in the use of the medication, blood pressure monitor, and medication and blood pressure log. The participant will be instructed to record the number of study treatment capsules and/or tablets and antihypertensive combination therapy tablets taken during the study period.

At follow-up visits, participants will be instructed to return any unused treatment, and the accuracy of the medication diary will be verified by comparing the data entered with the amounts of study treatment returned. If any discrepancies are noted, the investigator/coordinator should discuss the discrepancy with the participant and document the detailed explanation in the study records.

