### 8.3 Blood pressure measurement

Blood pressure readings will be taken by the researcher or a designated person qualified and trained in the study during the initial, follow-up, and final visits defined in the research schedule. DBP and SBP will be taken during each visit, with the patient seated, on the left arm, following WHO recommendations and using Korotkoff sounds.

Participants will be asked to measure and record their blood pressure at home during the study period using the calibrated digital blood pressure monitor provided by the researcher, following these recommendations for taking measurements:

- Take measurements on the left arm with the blood pressure monitor provided by the researcher.
- Sit in a comfortable chair for three to five minutes with the upper arm at heart level before taking a measurement.
- Do not exercise or engage in any other activity that requires cardiovascular effort prior to taking the measurement.
- Do not eat immediately before the reading, avoid consuming energy drinks such as coffee, tea, or soda.
- Take three readings at intervals of 1 to 2 minutes.
- Take the measurement once a day, at a time when you are not under stress, preferably when you wake up.
- Record the measurements in the blood pressure diary provided by the study.

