### DELIVERY OF SAMPLES

Samples of Nifedipino Comparador and Nifedipino Richmond will be delivered to the Méderi Pharmaceutical Service by letter and referral from Laboratorios Richmond Colombia S.A.S., indicating the number of corrugated boxes, the contents of each box, and the total number of samples of each product (reference and study samples).

A sufficient quantity of Nifedipine Comparator and Nifedipine Richmond must be delivered, duly blinded and controlled.

These samples must be listed by Méderi in the Inventory Traceability format. Research Products (F-FAR-33). In addition, a sealed envelope containing the identification letter for each sample (comparator Nifedipine and Richmond Nifedipine code) must be delivered to the Chemist responsible for the Pharmaceutical Service, indicating the protocol number, the name of the drug, the Center number, and the Investigator.

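### Appendix 6 codes the supplies by product and prints batch and expiry on every pack without saying they are masked, so one identified pack can reveal treatment for every patient-period sharing that batch or code

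*Protocol*

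**What the plan says.** Section 6.3 describes the trial as double-blind: packaging is identical, and the patient, the investigator and the clinical evaluation staff are not to know the assignment. Appendix 6 (Section 15.6) sets out how this is done.

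- **Coding** (Identification of samples): "The reference product samples and the Nifedipine Richmond samples will be assigned a code". On who holds it: "This code will only be known to the project leader on behalf of the Sponsor and the Pharmaceutical Chemist responsible for dispensing the medication".
- **Code-break material** (Delivery of samples): the chemist in charge of the pharmaceutical service receives "a sealed envelope containing the identification letter for each sample (comparator Nifedipine and Richmond Nifedipine code".
- **Blister**: "Each blister pack containing 10 capsules will have the batch number and expiry date printed in low relief". The list of items for the foil repeats both.
- **Box**: both products "will be packaged in folding boxes printed with the same information as the blister pack". The list that follows includes the product batch and the expiry date, and also "Participant Code and Visit Number". The blister list has no participant identifier.
- **Receipt and reconciliation** (Section 6.4.2): the center records batch, manufacturer and date at receipt. The investigator and the center are jointly responsible for accounting, reconciliation and treatment records.
- **Returns** (Section 6.5): at follow-up visits "participants will be instructed to return any unused treatment, and the accuracy of the medication diary will be verified". The investigator or coordinator discusses any discrepancy with the participant.
- **Outcome reading** (Section 8.3): clinic blood pressure is taken "on the left arm, following WHO recommendations and using Korotkoff sounds".

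**The concern.** Identical capsules and cartons protect the blind only if nothing printed on them separates the products. Appendix 6 calls for two printed values, batch and expiry, that ordinarily differ between two products. It describes no code below product level. The site's own receipt record pairs batch with manufacturer, and the investigator shares responsibility for the records in which that pairing can be found. The protocol thus asks a person to stay blind and also gives that person a share in the records that can undo the blind.

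The outcome can be affected by such knowledge. The primary endpoint (Section 9.3.1) is control below 140/90 mmHg at week 8, and the clinic readings rely on an observer listening for Korotkoff sounds. A small shift near the cut-off changes a patient's classification. Adverse events are elicited by oral questioning (Section 8.6.4). The sizing margin is 3 mmHg (Section 4.2.1). In a non-inferiority trial sponsored by the maker of the test product, readings nudged towards control on that product would favour the claim.

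**Working it through.** **The plan's own figure.** The 50 patients come from Section 4.2.1: margin 3 mmHg, SD of the paired difference 6 mmHg, one-sided 2.5%, power 90%.
- Normal approximation: n = (6 × 3.2415 / 3)² = 42.03, so 43 pairs.
- Noncentral t with n − 1 degrees of freedom: power is 90.0% at n = 44, which matches the stated 44.
- Losses: 44 / (1 − 0.10) = 48.9, so 49, against the stated 50.

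The figure reproduces to within one patient. It is not in dispute and serves only as the denominator below.

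**Is the code by product?** Identification of samples gives the two products a code, in the singular. Delivery of samples names the comparator code and the Richmond code as the content of the envelope. Neither place mentions a random kit number or pack number. Product-level coding is the natural reading, though it is not spelled out.

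**Can the labels separate the products?** Batch and expiry appear on every blister and every box. No sentence says that they are replaced by a study lot or made the same for both products. Nor does any sentence say that they are the manufacturer's own values. Product-specific batches are therefore an assumption.

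**Can a blinded person make the link?** Section 6.4.2 supplies the pairing of batch with manufacturer and the investigator's share in reconciliation. Section 6.5 brings unused medication back to visits at which the investigator or coordinator resolves discrepancies. Section 6.3 requires the investigator to be blind. Taken together, the link is possible; the protocol does not show that it will be made.

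**How far does one identified pack reach?** Assume product-specific batches, k equally used batches per product, and each patient staying within one batch of each product. Patients directly linked = 50 / k.

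| Batches per product (k) | Patients directly linked |
|---|---|
| 1 | 50 |
| 2 | 25 |
| 3 | 16.7, about 17 |
| 5 | 10 |

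In a two-treatment crossover, knowing the product in one period gives the other, so both periods of each linked patient are known. With labels and codes specific to the participant, the same event reaches 1 of 50.

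**Is one batch per product plausible?** Appendix 6 plans for 50 patients, 18 weeks and two capsules a day: 50 × 18 × 7 × 2 / 30 = 420 boxes in all, about 210 per product, with 500 boxes of each to be delivered. At one capsule a day the total is 210 boxes, about 105 per product. (Appendix 6 states a 60 mg daily dose and Section 4.5 states 30 mg; those passages need reconciling on their own account.) One batch per product is possible on either figure, but the number of batches is not stated.

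**The case against.** The strongest reply is that the text never says the printed batch is each product's own. The foil of both products carries the study code and the sponsor's name, so both go through study-specific packaging, and a common lot number may be intended. Packs are said to be identical and duly blinded. The code is restricted to two unblinded people and is not clearly among the printed items, and the box carries a participant code and visit number. Section 6.4.2 places receipt, storage, dispensing and inventory control in the pharmaceutical service, and Section 6.5 does not say who counts the returns.

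Much of this stands, and it makes the exposure conditional. It does not remove the gap. Restricting the code does not restrict the batch and expiry printed on the pack. A participant code beside a batch number does not stop packs being matched across patients. Section 6.4.2 still gives the investigator a share in reconciliation.

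Two stronger readings are tempting, and the documents support neither.
- A reader might infer that one emergency code break by itself exposes all 50 patients. Sections 8.4.2 and 15.3.2 send the request to the person responsible for randomisation and do not say that the envelope in Appendix 6 is opened. That route concerns one patient's allocation. It spreads only if someone then matches batches or codes across other patients' packs.
- A reader might infer that the label change at week 8 unblinds the patient. The switch is planned for everyone, and a changed number does not say which product came first.

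It can also be said that labels add little while Section 6.2 prints the sequence for patients 1 to 50 and defines the groups by product order. That is a fair remark about priority. It is a separate leak, and replacing the list would leave this one open.

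**Conclusion.** The point holds as a conditional weakness in the masking procedure. Appendix 6 describes product-level codes and puts batch and expiry on every pack without saying that they are masked or common to both products, and Sections 6.4.2 and 6.5 give a person who must stay blind a way to link batch to product. The reach of one identified pack is at most all 50 patients, and about 25, 17 or 10 directly linked patients with 2, 3 or 5 equally used batches per product. These figures assume product-specific printed batches, equal use, and each patient staying within one batch of each product; the protocol states none of these. The 50 is a ceiling, not an expected effect. No bias in mmHg or in the control rate can be derived from the documents, and a break cannot affect readings already taken. The change is still worth making, because the endpoint depends on an observer's reading against a fixed cut-off and the remedy is inexpensive.

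**What to change.** Amend Appendix 6 as follows:

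1. Replace the product codes with kit numbers specific to participant and period. The box already has a field for participant and visit.
2. Print one common packaging-lot number and one common expiry date, the earlier of the two, on the blisters and boxes of both products.
3. Keep the true batch-to-kit key with unblinded pharmacy or supply staff only. Apply the same restriction to the receipt and reconciliation records in Section 6.4.2, so that the investigator's share excludes anything that pairs batch with manufacturer.
4. Replace the envelope holding both products' codes with one sealed code-break per participant.

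The cost is label artwork, a kit list at packaging and the amendment itself, with no extra visits or patients. The one drawback is that the common expiry date may shorten the usable shelf life of one product. The sequence list printed in Section 6.2 must be dealt with separately for this change to have its full effect.
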